6.4 Study Assessments

The schedule of activities (SOA) details the study procedures:

Procedure	Screening and Enrollment (admission to +14 days from discharge)	Baseline (day of discharge +14 days) ³	6 weeks from randomization +/- 10 days	12 weeks from randomization +/- 10 days
Enrollment Visit (Inpatient)	SS			
Informed Consent	SS			
Inclusion/exclusion ¹	SS			
Randomization ²		CC		
App training & application-specific questionnaires	SS			
Demographics	SS			
Medical history		SS		
Follow Up Call & EHR review • Clinical events (death, hospitalization, other AEs) • Medications			SS	SS
HRQOL surveys	Participant	Participant	Participant	Participant
Nutritional Surveys	Participant		Participant	Participant
Daily self-monitoring (weight, blood pressure, activity monitor)			Participant-----	Participant
Final Status				SS/CC

Key: EHR = electronic health record, SS = study site, App = mobile application, CC = coordinating center

¹If screening/enrollment and baseline do not occur on the same day, re-confirm participant's eligibility at baseline.

²Randomization to occur remotely after participant completes HRQOL and Nutritional Surveys. The New York Heart Association (NYHA) questionnaire is not required for randomization.

³If a participant has been re-hospitalized prior to randomization, re-confirm participant's eligibility, complete a new Health History (Day of Discharge) form in the database with the most recent hospitalization data, and submit a Serious Adverse Event report.

7 Sample Size

Each intervention (clinical worsening intervention and dietary sodium application) will be treated as a standalone study in this 2x2 factorial trial, so there is no need to adjust the Type I error in our sample size calculation. The primary endpoint is a composite of time to event of all-cause death, time to event of HF rehospitalization, and change in HRQOL from baseline to 12 weeks. A win ratio^{1,2} will be estimated to compare the number of participants receiving the interventions who remain event free longer and have more favorable quality of life change than those not receiving the intervention. A win ratio of 1.0 indicates that both comparison groups have equivalent outcomes in terms of events and quality of life, while a win ratio > 1.0 indicates the intervention group has a favorable profile compared to the control group and < 1.0 indicates the intervention group has an unfavorable profile compared to the control group.

We hypothesize that the win ratio for the hierarchical endpoint in our pilot study will be 1.33 in favor of the clinical worsening intervention group, meaning that people receiving the intervention will be 33% more likely to experience favorable outcomes compared to the group not given the intervention. Assuming 10% dropout, 500 randomized participants (250 per main intervention arm) provides 80% power to show a win ratio of 1.30 (56.6% winners in the intervention group excluding ties) assuming a two-sided 5% type-one error rate).³⁴⁻³⁶ Figure 3 shows the sample size calculation for different win ratios at 80% power. After dropout, 225 participants per arm will have completed the study, producing 50,400 (225 x 224) permutations of paired comparisons. Identical reasoning is applied to the power and sample size necessary for the analysis of the dietary intervention.

A mediation analysis using structural equation modeling will be used to determine the proximal effect of the mobile phone apps results (M), “clinical worsening” and “dietary sodium intake”. Assuming 10% dropout, and an alpha of 0.05, this study’s 500 participants will provide at least 80% power to detect either a small standard effect size (0.14) on the association between each intervention and the proximal outcomes, and a medium effect size (0.39) on the association between proximal and distal outcomes, or a medium effect of each intervention on proximal results and a small effect on the association between proximal and distal outcomes.³⁷

There is insufficient power to detect an interaction effect of both interventions relative to the control.

8 General Analysis Considerations

8.1 Timing of Analyses

The final analyses of the ManageHF study were to be performed after all enrolled participants have completed study follow-up. The ManageHF study was prematurely terminated by the Data Safety and Data Monitoring (DSMB) Committee owing to insufficient enrollment.

8.2 Analysis Populations

All randomized participants will be included in the intent-to-treat (ITT) population, which is the analysis set used in all treatment comparisons of primary and secondary outcomes. All randomized participants who received an intervention (safety population) will be included in safety analyses.

8.3 Primary Endpoint Definition

The primary outcome is a hierarchical composite of time to all-cause death, time to first HF readmission, and change from baseline to week 12 in MLHFQ using the win ratio.

Death (from any cause) occurring during the study period will be reported by each site. We do not expect an intervention effect on death but are including the event because of its importance using this methodology.

Readmission is defined as admission to an inpatient unit or stay in an emergency department following discharge after the index hospitalization that results in at least a 24-hour stay.³⁰ Only admissions associated with events that occur on an emergency or unplanned basis will be considered as potential endpoints and then adjudicated. A HF readmission must have clinical manifestation of new dyspnea, orthopnea, paroxysmal nocturnal dyspnea, edema, pulmonary basilar rales/crackles, jugular venous distension, renal hypoperfusion with no other apparent cause or radiological evidence of acute HF and additional increased treatment with either intravenous HF medications (diuretics, inotropes, vasodilators) or mechanical or surgical intervention specifically directed at the treatment of HF. Only readmissions during the study period will be assessed.

The MLHFQ tool consists of 21 questions regarding patients' perception of the effects of HF on their daily lives.²⁹ The questions produce a total score of 0 to 105, with a higher score indicating poorer HRQOL. The MLHFQ will be collected at baseline, 6 and 12 weeks. A score change of 5 or more is considered a clinically significant difference for the hierarchical composite endpoint.

Following the unmatched pairs win ratio method of Finkelstein and Schoenfeld,³⁴⁻³⁶ each participant receiving intervention will be compared to each participant not receiving intervention, resulting in $N_i \times N_{ni}$ pairwise comparisons, where N_i is the sample size for the intervention arm, and N_{ni} is the sample size for the non-intervention arm. For each comparison, "winners" will be determined according to the table below, starting with scenario 1.

Scenario	Time to all-cause death	Time to HF readmission	Change in MLHFQ	Win/loss
1	Low			Loss
	High			Win
2	Tie or both alive	Low		Loss
		High		Win
3	Tie or both alive	Tie or both not hospitalized	Comparator	Loss
			12-week change ≥ 5 points better than comparator	Win
4	Tie or both alive	Tie or both not hospitalized	Comparator	Tied
			12-week change within 5 points of comparator's 12-week change	Tied

Within each pairing, the participant with the longest survival time is counted as the "winner" of that pairing. The win ratio is the number winners divided by the number of losers associated with the intervention. The estimate of the win ratio will be calculated, and its 95% confidence interval will be calculated using bootstrap methods. The test for intervention effect is a nonparametric rank sum test. In the event there is more than a 10% loss-to-follow-up, sensitivity analyses based on multiple imputation of the primary outcome will be conducted. However, if some lost or withdrawn participants were readmitted to hospital, a determination may still be possible for the win ratio statistic.

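### SAP 8.3 forces a decision on pairs with one event and one earlier censored time; the win-ratio rule needs an explicit shared-follow-up condition

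*SAP*

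**What the plan says.** The scoring table in SAP 8.3 (the same as Table 2 in Protocol 9.3.2) gives the loss to the lower time and the win to the higher time, first for death and then for HF readmission. The condition for leaving the death tier is "Tie or both alive"; the readmission tier has a matching condition. The text below the table adds that in every pair "the participant with the longest survival time is counted as the" winner.

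Three other statements in SAP 8.3 bear on the point:
- It names its method: "Following the unmatched pairs win ratio method of Finkelstein and Schoenfeld".
- On people who leave, it says: "if some lost or withdrawn participants were readmitted to hospital, a determination may still be possible for the win ratio statistic".
- On missing data, it says: "In the event there is more than a 10% loss-to-follow-up, sensitivity analyses based on multiple imputation of the primary outcome will be conducted".

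SAP 8.6 adds multiple imputation at the statistician's discretion. Neither document defines a time for a censored participant, a common follow-up limit, or a score for a pair in which one member leaves before the other's event.

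The final visit is set at "12 weeks from randomization +/- 10 days" (SAP 6.4), that is, day 74 to day 94. Protocol 7.2 has sites ask withdrawing participants for permission to keep following their health record. Protocol 7.3 requires a record review at 12 weeks.

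**The concern.** The pass-on conditions protect pairs in which nobody has an event: the longer-followed member does not win on time alone. They do not protect a pair with one event and one shorter, censored time. That pair is neither tied nor jointly event-free, so the table must decide it, and the only times available are the event time and the earlier departure time. The shorter time loses, although it is unknown whether its owner outlived the other.

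Early departure then counts as a bad outcome, and the win ratio partly measures who stayed under observation. If departure differs by arm, the primary estimate moves away from 1 with no treatment effect. The arms differ in how many push notifications they receive, so different departure rates are conceivable; the documents neither predict nor report any. Separately, two statisticians could follow the same SAP and compute different win ratios.

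**Working it through.** **1. The plan's own figure.** The documents give no figure for the scoring rule. The nearest is the sample size: 500 randomized, 10% dropout, 225 per arm, 80% power at 56.6% winners. The two-proportion formula with p1 = 0.566 and p2 = 0.434 gives n = [1.96·√(2·0.5·0.5) + 0.8416·√(0.566·0.434 + 0.434·0.566)]² / 0.132² = (1.3859 + 0.5899)² / 0.017424 = 224.05, rounded up to 225 per arm, with 80.2% power; 450/0.9 = 500. The figure reproduces by this formula. Whether the formula suits a win ratio is a separate question, and the calculation does not depend on how censored pairs are scored.

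**2. Single pairs.**

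| Pair | Literal rule | Shared follow-up |
|---|---|---|
| Left alive day 20 vs died day 60 | leaver loses | undecided, passes on |
| Left event-free day 20 vs HF readmission day 60 | leaver loses | undecided, passes on |

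The first case rests on the table and on the longest-survival sentence. The second rests on the table alone, because that sentence covers survival only. The visit window can produce such a pair with no dropout: event-free follow-up ending on day 75 against a readmission on day 80.

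**3. Simulation inputs.**
- From the documents: 12-week HF readmission of 19-26% (Protocol 2.2 reports 19.3% and 26.2% in the pilot), follow-up ending on days 74-94, and a 5-point MLHFQ threshold.
- Assumed: 12-week death of 2-10%, MLHFQ change SD 22, dropout times uniform, and leavers lost to tiers 1 and 2 as well as to MLHFQ.

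Every between-arm pair was scored under both rules.

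**4. Share of pairs whose score changes.** The visit window alone, without dropout: 0.96%. At 10% overall dropout: 2.3-3.6%, of which 0.4-0.6% of all pairs flip between win and loss. At the planned size there are 250 × 250 = 62,500 pairs, so 2.3-3.6% is about 1,440 to 2,250 pairs. The final number of participants is not in the documents.

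**5. Win ratio with no true effect, literal minus shared** (dropout is intervention/control):

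| Death / readmission | 10%/10% | 5%/15% | 15%/5% | 10%/30% | 30%/10% |
|---|---|---|---|---|---|
| 2% / 19% | -0.001 | +0.023 | -0.024 | +0.060 | -0.051 |
| 5% / 23% | +0.004 | +0.025 | -0.031 | +0.066 | -0.058 |
| 10% / 26% | +0.002 | +0.031 | -0.033 | +0.079 | -0.069 |

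For example, in the last row at 10%/30%: 1.116 - 1.037 = +0.079. A separate run with 5% versus 25% withdrawal, death 5-9% and readmission 20-26% gave 1.06-1.07 under the literal rule against 1.00 under shared follow-up.

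**6. With a true benefit and 10%/10% dropout.** The win ratio falls from 1.302 to 1.284, from 1.228 to 1.208 and from 1.235 to 1.219, a dilution of about 0.02.

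**The case against.** The strongest reply is that the literal reading is not the intended one. The table's columns are times to events, and a person who left alive has no time to death to enter. The section names a method that by construction decides a pair only on what is known for both members. Its sentence on lost or withdrawn participants also implies that some pairs may stay undetermined. A reader might infer from the literal rule that the primary win ratio is in fact mis-scored. The documents do not support that, because they do not show how the rule was programmed.

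This stands as to intent, but it does not supply a rule. Naming a method does not amend a table that points elsewhere, and the sentence on leavers covers only those who were readmitted. If a censored person has no entry, a pair with one event fits no row at all. If being event-free is coded as the longest possible time, the day-20 leaver beats the day-60 death, and the error runs the other way.

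The second reply is that tier 1 and 2 censoring should be limited. Record review and continued health-record access can capture deaths and readmissions after contact is lost, so much dropout may affect only MLHFQ. This also stands. The simulated dropout effects are therefore high for a given dropout rate, though permission may be refused and outside admissions missed.

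A reader might also infer that the early termination cut follow-up short. SAP 8.1 attributes the stop to insufficient enrollment, and neither that section nor SAP 14 says that anyone already enrolled was censored.

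**Conclusion.** The concern holds as a defect in the written rule. Applied as written, SAP 8.3 and Protocol 9.3.2 would mis-score pairs with one event and an earlier censored time, contrary to the method they name. Whether the rule was applied that way is not shown.

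The size is modest: about 1% of pairs from the visit window alone and about 2-4% at 10% dropout. Null bias is negligible when dropout is balanced. It reaches 0.02-0.03 in the win ratio for a 5% versus 15% split, and 0.05-0.08 only for splits as wide as 5% versus 25% or 10% versus 30%, always against the arm that loses more people. The plan assumes 10% dropout overall and gives no reason to expect the wider splits. These sizes rest on the assumed death rate, dropout timing and MLHFQ SD. The point should be fixed because it concerns the primary endpoint and the correction is nearly free.

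**What to change.** In SAP 8.3, replace the longest-survival sentence, and extend the table's pass-on conditions to match, with wording such as:

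> A death, or a first HF readmission, decides a pair only if it occurs while both members are under observation, that is, within the shorter of the two follow-up times, truncated at day 84 from randomization. Follow-up obtained by record review counts as observation time. A pair not decided at a tier passes to the next tier. If the week-12 MLHFQ is missing for either member, a pair that reaches the third tier is scored as a tie in the primary analysis. Multiple imputation is the sensitivity analysis.

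Day 84 from randomization follows the anchor in the SAP schedule. The protocol schema (section 1.2) counts follow-up from discharge, so the two must be reconciled. Record the change in SAP 14 as a departure from Protocol 9.3.2.

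The cost is a few sentences, the matching program change and no new data. Somewhat more pairs pass to the third tier or tie. In the null simulations with 10%/10% dropout, ties rise from 20.0% to 21.9%, from 17.6% to 20.0% and from 15.2% to 18.2%, that is, by about 2 to 3 percentage points.

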8.4 Stratification Factors

An exploration of stratification factors was planned in the protocol: site, sex, race, and HF type (HFpEF versus HFrEF). Additionally, the protocol indicated an exploration of whether there is a signal for an interaction effect for the use of both mobile applications. These analyses will not be completed given the early termination of the study and the final available number of participants (see Section 14 below).

8.5 Multi-center Studies

This is a multi-center study. Site effects will not be investigated given the early termination of the study and the final available number of participants (see Section 14 below).

8.6 Missing Data

Assessment of the extent of missing data and its mechanism will be explored for the primary endpoints using the ITT analysis set. Graphical and numerical descriptive methods will be used to summarize the primary outcome over time, by intervention group and overall. We will begin by assuming missing at random and employ multiple imputation methods to handle missing data at the discretion of the study statistician.

8.7 Data Monitoring and Interim Analyses

No formal interim analyses are planned for this study. The study is overseen by a Data and Safety Monitoring Board (DSMB) that reviewed the pooled and by-treatment subject disposition, study conduct, and safety data approximately every 6 months.

8.8 Multiple Testing

Statistical testing is conducted at the 0.05 significance level using two-tailed tests; two-sided p-values are reported unless otherwise stated.

9 Summary of Study Data

Continuous variables will be summarized using descriptive statistics including n, mean, median, standard deviation, range (e.g., minimum, and maximum). Categorical variables will be summarized using counts and percentages. Summaries will be provided by treatment group and overall.

9.1 Subject Disposition

Participant disposition will be summarized descriptively. The number and percentage of participants randomized, completed, and withdrawing, along with reasons for withdrawal, will be tabulated and summarized in a consolidated standards of reporting trials (CONSORT) diagram, both overall and by treatment group. The number of participants in each analysis population will be reported. Other disposition and study conduct information, including major protocol violations will be summarized. Duration of the study follow-up will be summarized overall and by treatment group.

9.2 Derived variables

Derived variables include:

1. Treatment groups
 1. Dietary intervention (Yes/No)
 2. Clinical Worsening (Yes/No)
2. Win Ratio - The primary outcome is a hierarchical composite of time to all-cause death, time to first HF readmission, and change from baseline to week 12 in MLHFQ using the win ratio.
3. Change in MLHFQ over 12 weeks.

9.3 Protocol Deviations

A protocol deviation is any noncompliance with the clinical trial protocol, GCP, or MOP requirements. The noncompliance may be either on the part of the participant, the investigator, or the study site staff. Protocol deviations are provided in a table listing the frequency of each protocol deviation category.

9.4 Demographic and Baseline Variables

All the following demographic and baseline variables will be summarized overall and by treatment group.

Demographic characteristics will be summarized: age (years); age (18-35, 36-50, 51-65, 66 to 80, >80 years, missing); sex at birth (male, female, not reported); ethnicity (Hispanic or Latino, not Hispanic or Latino, unknown or not reported); race (white, black or African American, Asian, American Indian or Alaskan Native, Native Hawaiian or Other Pacific Islander, Multi Race, Unknown or Not Reported).

Baseline characteristics will be summarized: heart failure type (reduced ejection fraction, preserved ejection fraction); NYHA (category 1, category 2, category 3, category 4, missing); baseline MLHFQ score; baseline sodium screener (mg/dL); heart rate; systolic blood pressure.

9.5 Compliance with Standard of Care

After the device set up, participants' use of the mobile app will be tracked within the app, but study staff will not intervene for lack of interaction with the mobile app. Use of the blood pressure monitor, scale, and watch will also not be monitored by the sites and the study team will not intervene for lack of use.

10 Analyses

10.1 Statistical Hypotheses

There are two primary hypotheses for the 2x2 factorial study that investigate the main effects of each of the 2 interventions:

1. The use of the clinical worsening intervention will reduce deaths and HF readmissions and improve health-related quality of life compared to not using the intervention.
2. The use of the dietary sodium intervention will reduce deaths and HF readmissions and improve health-related quality of life compared to not using the intervention.

10.2 Primary Analysis of Primary Endpoint

The primary outcome is a composite of death, HF readmission, and change in quality of life using the win ratio method, which incorporates a hierarchy of clinical prioritization on event occurrence. The win ratio is the number winners divided by the number of losers associated with the intervention. The estimate of the win ratio will be calculated, and its 95% confidence interval will be calculated using bootstrap methods. The win ratio will be summarized overall and by each treatment group (dietary intervention group yes/no, clinical worsening intervention group yes/no). The test for intervention effect is a nonparametric rank sum test.

10.3 Primary Analysis of Secondary Endpoints

Secondary endpoints will be summarized overall and by treatment groups: time to all-cause mortality, time to first heart failure readmission, and change in MLHFQ over 12 weeks.

Simple Cox proportional hazard models will be used to assess time to all-cause mortality and time to first heart failure readmission as a function of treatment group assignments. Hazard ratios and 95% confidence intervals will be reported. Kaplan-Meier curves will be used to visually assess time to all-cause mortality and time to first heart failure readmission by treatment group assignments.

Simple linear regression models will be used to assess the outcome of change in MLHFQ over 12 weeks. Beta coefficients and 95% confidence intervals will be reported. Estimated marginal means for each treatment group will be computed with 95% confidence intervals. The outcome of change in MLHFQ over 12 weeks will be visually assessed with side-by-side box plots (by each treatment group status).

11 Safety Analyses

The number and proportion of participants with SAEs, (including segregation of those involving deaths), treatment-emergent AEs, and discontinuation of study intervention due to AEs will be presented, overall, and by randomization group (both intervention, diet intervention only, clinical worsening intervention only, neither intervention). These presentations will be descriptive, with no formal inferential methods used. The JITAs are not expected to pose a great risk to participant safety. Thus, no specific rules for halting study enrollment or study interventions for safety are specified.

In accordance with clinicaltrial.gov reporting requirements, the following tables are required and will be provided:

- All-Cause Mortality: A table of all anticipated and unanticipated deaths due to any cause, with the number and frequency of such events by arm or comparison group of the clinical study.
- Serious Adverse Events: A table of all anticipated and unanticipated serious adverse events, grouped by organ system, with the number and frequency of such events by arm or comparison group of the clinical study. (See Adverse Events definition below).
- Other (Not Including Serious) Adverse Events: A table of anticipated events of special interest (not included in the serious adverse event table) with the number and frequency of such events by arm or comparison group of the clinical study.

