2.1 STUDY RATIONALE

Scope of Heart Failure

By 2030, over 8 million Americans will have heart failure (HF), and HF will account for \$69 billion/year in medical expenditures. Much of this societal cost is related to hospitalizations for worsening HF, which also take a terrible toll on individuals. Approximately one-third of patients who survive hospitalization for HF die within a year. Hospital readmissions are common, as more than one-fifth of patients with HF are readmitted within 30 days of initial discharge. These recurrent hospital stays not only increase the risk of death, but also markedly worsen health-related quality of life (HRQOL), contribute to functional decline, and increase the risk for long-term institutionalization. Hospitals also suffer the consequences; HF is the primary driver for federal 30-day readmission penalties, which now exceed \$500 billion/year. Reducing HF readmissions is thus an essential goal across the healthcare spectrum from patients to payers.

Efforts to Reduce Readmissions

Most U.S. hospitals now have dedicated quality improvement teams to reduce readmissions in patients with HF.⁸ These efforts typically cover four domains: enhanced patient education, increased use of evidence-based HF therapies, timely post-discharge follow-up, and improved communication between inpatient and outpatient healthcare providers.⁹ Although based on a strong rationale, these initiatives have produced mixed results.¹⁰ A recent slight decline in risk-adjusted 30-day readmissions has plateaued, and this improvement partially relates to changes in risk coding¹¹ rather than definitive improvement in outcomes. Even more concerning, both crude and risk-adjusted 30-day mortality in HF have gradually increased over this timeframe.^{4,12} It is clear that new approaches are needed to improve post-discharge outcomes in patients with HF.

Rationale for an Intervention During an Episode of Clinical Worsening

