We developed a mobile application that can effortlessly assist in self-monitoring, ultimately driving self-management in HF. Version 1 of the application provided patients a health status indicator (HSI) using standard stop light color concept (green, yellow, red) and a message explaining the meaning of the HSI. A deterministic algorithm, based on a daily survey and the change in patient weight compared to dry weight, produces the number for the HSI. See figure 2 for a depiction of the HSI page. We studied this intervention in a randomized clinical trial, which was Aim 1 of an R21 funded by the National Institute on

Aging. We hypothesized that the HSI would accomplish enhanced self-management and improve HRQOL. HF patients at hospital discharge were randomized to the App or usual care (No App) in a 1:1 fashion and followed for 12 weeks. The MLHFQ was collected at baseline, 6 weeks and 12 weeks and HF readmissions were collected over the 12 weeks. Eighty-three patients were enrolled and completed all baseline assessments. Baseline characteristics were similar between groups, except HF type. The average age is 60.2 and 62 years in the App and No App arms, respectively. Most patients were NYHA class III, 58% had ischemic heart disease as the origin of HF, 57% had atrial fibrillation and 35% were female. The App group had a reduced MLHFQ at 6 weeks (p=0.039) but not at 12 weeks (p=0.778) compared to control. The time to first HF readmission was not statistically different between the two groups, but in favor of the App group (App 26.2% vs. No App 19.3%, HR 0.89, 95% CI 0.39-2.02, p=0.781).

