5.2.2 Secondary Endpoints Endpoint

1. Time to all-cause mortality
2. Time to first HF readmission
3. Change in MLHFQ over 12 weeks

6 Study Methods

[figure not shown]

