6.2 Inclusion-Exclusion Criteria and General Study Population

All eligibility criteria must be met in order to participate in this study:

1. Age 18 years and older at screening
2. Currently admitted or discharged from the hospital within the last 14 days with a diagnosis of acute or acute on chronic decompensated HF.
3. Based on one of the EF criteria (LVEF within 12 months of randomization. BNP or NT-proBNP criteria within 30 days prior to randomization):
 - Left ventricular ejection fraction (LVEF) $\leq 40\%$.
 - LVEF $>40\%$ and BNP $> 175 \text{ pg/ml}$ or NT-proBNP $> 700 \text{ pg/ml}$. Thresholds for NT-proBNP and BNP for LVEF $> 40\%$ will be corrected for body mass index (BMI) using a 4% reduction per BMI unit over 25 kg/m^2 .*
4. Have a personal physician for follow-up
5. A smartphone with a compatible Apple or Android operating system installed and able to download and use ManageHF including accepting all permissions
6. A valid email address
7. Fluent in spoken and written English
8. Signed written informed consent. (Note that each participant must be able to consent for themselves.)

*BNP threshold for eligibility:

BMI	BNP LVEF >40	NT- ProBNP LVEF >40
25	175	700
26	168	672
27	161	644
28	154	616
29	147	588
30	140	560
31	133	532
32	126	504
33	119	476
34	112	448
35	105	420
36	98	392
37	91	364
38	84	336
39	77	308
40	70	280
41	63	252
42	56	224
43	49	196
44	42	168
45	35	140
46	28	112
47	21	84
48	14	56
49	7	28

An individual who meets any of the following criteria will be excluded from participation in this study:

1. Contraindication to recommending a sodium restriction diet
2. Scheduled intervention for primary valvular heart disease will occur during the study period
3. Cardiac resynchronization therapy (CRT) within 3 months prior to screening or current plan to implant CRT device during the study period.
4. Dialysis
5. Previous cardiac transplantation or implantation of a ventricular assistance device or similar device.
6. Listed status 1, 2 or 3 for heart transplant
7. Implantation of a ventricular assistance device is expected within 3 months after randomization
8. Non-cardiac illness with expected survival of less than 3 months
9. Discharge to a setting other than home
10. Requirement for chronic inotropic therapy (e.g. milrinone, dobutamine)
11. Inability to use Withings devices due to equipment limitations or contraindications
12. Currently pregnant or intend to become pregnant during the study period.

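### SAP 10.3 plans Kaplan-Meier curves for first HF readmission without saying how prior deaths are handled; cumulative incidence would show the actual readmission risk, a modest improvement

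*SAP*

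**What the plan says.** SAP 5.2.2 lists "Time to first HF readmission" as a secondary endpoint, separate from all-cause mortality, so death is not part of the event. For its analysis SAP 10.3 says: "Simple Cox proportional hazard models will be used to assess time to all-cause mortality and time to first heart failure readmission", with hazard ratios and 95% confidence intervals. For its display the same section says: "Kaplan-Meier curves will be used to visually assess time to all-cause mortality and time to first heart failure readmission by treatment group assignments".

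Protocol 9.3.2 refers only to survival methods for time-to-event outcomes. Neither document mentions competing risks or cumulative incidence, and neither states what happens to a participant who dies before being readmitted. The table and figure shells are in a separate file named in SAP section 17, which is not among the documents reviewed.

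Deaths are collected. SAP 8.3: "Death (from any cause) occurring during the study period will be reported by each site". The same section states the expectation for mortality: "We do not expect an intervention effect on death but are including the event because of its importance using this methodology".

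**The concern.** Kaplan-Meier suits all-cause mortality, which nothing competes with. First HF readmission is different, because a participant who has died cannot be readmitted. If deaths are censored, the estimator treats the dead as though they remained exposed to the same readmission hazard as the survivors. One minus Kaplan-Meier then describes readmission in a population where nobody dies, and it lies above the proportion actually readmitted whenever a death precedes a readmission.

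What is at stake is the absolute level a reader takes from the curve. SAP section 14 drops 30-day HF hospitalization and days alive and out of hospital, so this figure is the only planned display of readmission over time, and it does not account for death.

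The missing rule also leaves the Cox result without a fixed meaning. With deaths censored, it is a cause-specific hazard ratio. If the dead were instead kept in the risk set to week 12, both the curve and the ratio would describe something else. Two programmers could follow SAP 10.3 and report different quantities.

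**Working it through.** The documents give no planned readmission risk, mortality rate or precision for these curves, so there is no figure to reproduce. The check asks how far one minus Kaplan-Meier would sit above the actual risk if deaths are censored.

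**Inputs**

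- Readmission risk R: 19.3% to 26.2%, from the pilot in Protocol 2.2 ("App 26.2% vs. No App 19.3%, HR 0.89, 95% CI 0.39-2.02, p=0.781"). The percentages favor the control group while the hazard ratio and surrounding text favor the App group, so they serve only as a range.
- Mortality D: Protocol 2.1 says "Approximately one-third of patients who survive hospitalization for HF die within a year". At a constant hazard, 12-week mortality is 1 − (2/3)^(12/52) = 8.9%. Protocol 4.3 describes higher risk early after discharge, which would raise this. Exclusions such as "Non-cardiac illness with expected survival of less than 3 months" would probably lower it. The range 1% to 15% is therefore an assumption.
- Group size: 250 × 0.90 = 225 per group, as planned. The trial stopped early and the SAP does not give the final number, so 50 per group is added purely as an illustration.

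**Formulas** (constant cause-specific hazards over 12 weeks, time unit 12 weeks; the death hazard is taken to be the same before and after readmission)

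- Death hazard: d = −ln(1 − D)
- Cumulative incidence: CIF = r/(r + d) × (1 − exp(−(r + d)))
- Kaplan-Meier with deaths censored: 1 − KM = 1 − exp(−r)

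**Example.** With D = 8.9%, d = 0.0932. Setting CIF = 19.3% gives r = 0.2254, because 0.2254/0.3186 × (1 − exp(−0.3186)) = 0.7075 × 0.2728 = 0.193. Then 1 − KM = 1 − exp(−0.2254) = 20.2%, an overstatement of 0.9 points.

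**Overstatement over the range**

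| 12-week mortality | 1 − KM when CIF = 19.3% | Excess (points) | 1 − KM when CIF = 26.2% | Excess (points) |
|---|---|---|---|---|
| 1% | 19.39% | 0.09 | 26.33% | 0.13 |
| 2% | 19.49% | 0.19 | 26.45% | 0.25 |
| 5% | 19.78% | 0.48 | 26.84% | 0.64 |
| 8.9% | 20.18% | 0.88 | 27.37% | 1.17 |
| 15% | 20.84% | 1.54 | 28.26% | 2.06 |

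**Against sampling error.** In 4,000 simulated data sets at 8.9% mortality, the standard error of one group's 12-week estimate, by either method, was about 2.7 to 3.0 points at 225 per group and about 6 points at 50.

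**Between-group difference.** The first three rows use a hazard ratio of 0.89 and a control CIF of 19.3%. The last uses equal readmission hazards.

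| Mortality, control / intervention | Difference by KM (points) | Difference by CIF (points) |
|---|---|---|
| 8.9% / 8.9% | 2.00 | 1.92 |
| 8.9% / 6% | 2.00 | 1.66 |
| 6% / 8.9% | 1.98 | 2.18 |
| 8.9% / 4.45%, HR 1 | 0 (both 24.0%) | 23.0% against 23.5% |

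With equal mortality the two displays agree to within 0.1 point. With unequal mortality they part by 0.2 to 0.5 points. In the last row it is cumulative incidence that separates the groups although the readmission hazards are identical.

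**The case against.** The strongest reply is that the SAP never says deaths are censored. It leaves the rule out, and the unseen figure shells might supply it. A reader might infer that a wrong estimator has been specified; the text supports only that the handling of deaths is unstated. That stands, and the size given here is conditional on the default.

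Second, the curves are a visual aid to a secondary endpoint that Protocol 9.3.1 treats as hypothesis-generating. The named estimates are hazard ratios, and no Kaplan-Meier 12-week risk is planned as a reported number. With deaths censored, Cox validly estimates the cause-specific hazard ratio, and Kaplan-Meier is its customary companion plot. This stands and limits the point to the absolute level read from the figure.

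Third, a reader might infer that the display could create or hide a treatment difference. The documents do not support that as an expectation: no effect on death is anticipated, and under equal mortality the contrast hardly moves. If deaths were unequal, by chance or otherwise, the two displays would differ by a few tenths of a point, and neither is simply the unbiased one. They answer different questions.

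What survives is that the rule is missing, and that someone reading the curve as the proportion readmitted would read it slightly high.

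**Conclusion.** The point holds as a minor improvement to the analysis plan. If deaths before readmission are censored, one minus Kaplan-Meier overstates the 12-week HF readmission risk by about 0.5 to 1.2 points at 5% to 9% mortality, and by 0.1 to 2.1 points over 1% to 15%. This is below the sampling error of a single curve at the planned size, and further below it after early termination. A group with no death before readmission has no overstatement.

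The size rests on constant hazards, on readmission of 19.3% to 26.2%, and on mortality scaled from a one-third annual figure. Only deaths that precede readmission count, so the overstatement is smaller if mortality is concentrated after readmission.

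A reader might go further and infer that the secondary hazard ratio or the primary result is biased. Neither follows. The Cox ratio remains valid for the readmission hazard once it is labelled, and the win ratio ranks death above readmission, so it does not depend on this display. Sample size and type I error are untouched.

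**What to change.** In SAP 10.3:

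1. State that a death before HF readmission is treated as a competing event.
2. Keep Kaplan-Meier for all-cause mortality.
3. For first HF readmission, plot Aalen-Johansen cumulative incidence by treatment group, beside the mortality curve.
4. Keep the Cox model, state that follow-up is censored at death in it, and label its result a cause-specific hazard ratio.

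The cost is a few lines of SAP text and a different plotting procedure. Death data are already collected, and no participants or alpha are needed. The drawback is one of interpretation: cumulative incidence depends on both the readmission and the death hazards, so the curves may not mirror the Cox hazard ratio. This is why the mortality curve belongs beside them.
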